6.3.1.2 Sensitivity Analysis

The primary analyses will be repeated using the Immunogenicity Set as a sensitivity analysis. Refer to Immune Estimand 1b and 2b in [Table 12](#).

6.3.1.3 Subgroup Analysis

To assess the consistency of immunogenicity response of mRNA-1010 across subgroups, subgroup analysis of the co-primary endpoints will be conducted by subgroups defined by age group 1, age group 2, prior influenza vaccine status, race, sex, and BMI category (see [Table 5](#)), based on PP Immunogenicity Set. For each subgroup category, the co-primary immunogenicity endpoints will be analyzed using the same statistical methods as for primary analysis. Additional details are documented in [Section 4.2](#).

If the number of participants in a subgroup is less than 10% of sample size in the analysis set, it may be combined with other subgroups for the subgroup analyses.

6.3.2 Analyses of Secondary Immunogenicity Endpoints

- Analysis of GMTs of anti-HA antibodies as measured by HAI against vaccine-matched influenza A strains on Day 29 (superiority and super-superiority testing)

If the non-inferiority is demonstrated for A strains only, superiority of mRNA-1010 relative to the active comparator against vaccine-matched influenza A strains at Day 29 will be tested at a two-sided $\alpha_1=2.5\%$ level. If the non-inferiority is demonstrated for both A and B strains, superiority of mRNA-1010 relative to the active comparator against vaccine-matched influenza A strains at Day 29 will be tested at a two-sided $\alpha_1=5\%$ level.

The same ANCOVA model for primary analysis will be applied. The superiority of GMT in participants who received mRNA-1010 compared to GMT in participants who received active

comparator will be demonstrated by the lower bound of the $(100\% - \alpha_1)$ CI % of the GMR ruling out 1 (lower bound > 1).

If superiority is demonstrated based on lower bound of $(100\% - \alpha_1)$ CI % of $GMR > 1$, the super-superiority of GMT in participants who received mRNA-1010 compared to participants who received active comparator will then be evaluated based on a lower bound of $(100\% - \alpha_1)$ CI % of the $GMR > 1.5$.

- Analysis of SCRs of anti-HA antibodies as measured by HAI against vaccine-matched influenza A strains on Day 29 (super-superiority testing)

Rate of seroconversion is defined as the proportion of participants with either a pre-vaccination HAI titer $< 1:10$ and a post-vaccination titer $\geq 1:40$ or a pre-vaccination HAI titer $\geq 1:10$ and a minimum 4-fold rise in post-vaccination HAI antibody titer. If super-superiority has been demonstrated based on GMT, the SCR of the vaccine-matched influenza A strains at Day 29 between the vaccination groups will be compared. The Miettinen-Nurminen's method will be used to calculate the $(100\% - \alpha_1)$ CI for the difference in SCRs. For the A strains, the super-superiority of SCR will be considered demonstrated if the lower bound of the $(100\% - \alpha_1)$ CI % of SCR difference is $> 10\%$.

In addition, the number and percentage of participants that reached seroconversion at each time point will be provided with 2-sided 95% CI using the Clopper-Pearson method.

- Analysis of frequency of participants with an HAI titer $\geq 1:40$ on Day 29

The number and percentage of participants with an HAI titer $\geq 1:40$ post-injection due to vaccination will be provided with 2-sided 95% CI using the Clopper-Pearson method.

- Analysis of GMT of vaccine-matched strain-specific anti-HA antibodies on Day 29 as measured by HAI

Descriptive statistics (n, median, min, max) will be provided as described in the immunogenicity primary analysis ([Section 6.3.1.1](#)).

- Analysis of GMFR of vaccine-matched strain-specific anti-HA antibodies comparing Day 29 to Day 1 (baseline) as measured by HAI

Descriptive statistics (n, median, min, max) will be provided for the GMFR of HAI titers with corresponding 95% CI at Day 29 over baseline. The 95% CIs will be calculated based on the t-distribution of the log-transformed values then back transformed to the original scale for presentation. In addition, the GMFR with corresponding 95% CI will be plotted at Day 29.

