3. OBJECTIVES AND ENDPOINTS

The objectives which will be evaluated in this study and endpoints associated with each objective are provided in [Table 2](#).

Table 2: Study Objectives and Endpoints

Objectives	Endpoints
Primary	

 To evaluate the humoral immunogenicity of mRNA-1010 relative to that of an active comparator against vaccine-matched influenza A and B strains at Day 29 	
 GMT at Day 29 as measured by HAI assay Proportion of participants reaching seroconversion at Day 29 as measured by HAI assay

 To evaluate the safety and reactogenicity of mRNA-1010 	
 Frequency and grade of each solicited local and systemic reactogenicity AR during a 7-day follow-up period post vaccination Frequency and severity of any unsolicited AEs during the 28-day follow-up period post vaccination Frequency of any SAEs, AESIs, MAAEs, and AEs leading to discontinuation from Day 1 through Day 361 (Month 12)/EoS
Secondary	

 To further evaluate the immunological response of mRNA-1010 (for superiority) relative to an active comparator against vaccine-matched influenza A virus strains at Day 29 	
 GMT at Day 29 as measured by HAI assay Proportion of participants reaching seroconversion at Day 29 as measured by HAI assay

 To evaluate relative vaccine efficacy to prevent influenza caused by any strain of influenza virus 	
 First episode of RT-PCR–confirmed protocol-defined ILI that begins at least 14 days postvaccination through Day 181 (Month 6)/end of influenza season caused by any strain of influenza virus regardless of antigenic match to the strains selected for the seasonal vaccine First episode of RT-PCR–confirmed Centers for Disease Control and Prevention (CDC)–defined ILI that begins at least 14 days postvaccination through Day 181 (Month 6)/end of influenza season caused by any strain of influenza virus regardless of

Objectives	Endpoints

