The null hypothesis H^3_0 : immunogenicity response to mRNA-1010 compared to that in participants who received the active comparator, as measured by GMR at Day 29 using HAI assay, is ≤ 1 for each individual A strain (H1N1 and H3N2). The superiority in GMT in participants who received mRNA-1010 compared to that of participants who received active comparator will be demonstrated by the lower bound of the $(100\% - \alpha)$ CI of the GMR ruling out 1 (lower bound > 1) for both individual A strains.

Once the success criteria of hypothesis H^3_0 are met, the next null hypothesis to be tested is H^4_0 : immunogenicity response to mRNA-1010 compared to that in participants who received the active comparator, as measured by GMR at Day 29 using HAI assay, is ≤ 1.5 for each individual A strain (H1N1 and H3N2). The super-superiority in GMT in participants who received mRNA-1010 compared to that of participants who received active comparator will be demonstrated by the lower bound of the $(100\% - \alpha)$ CI of the GMR ruling out 1.5 (lower bound > 1.5) for both individual A strains.

If the success criteria of hypothesis H^4_0 are met, the last null hypothesis to be tested is H^5_0 : immunogenicity response to mRNA-1010 compared to that in participants who received the

active comparator, as measured by seroconversion rate difference at Day 29 using HAI assay, is $\leq 10\%$ for each individual A strain (H1N1 and H3N2). The super-superiority of seroconversion rate in the mRNA-1010 group compared to that in the active comparator group will be demonstrated by the lower bound of the $(100\% - \alpha)$ CI of the seroconversion rate difference ruling out 10% (lower bound $> 10\%$) for both individual A strains.

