9.6.2 Multiplicity

To control the overall Type I error for the study, a hierarchical testing strategy will be used to test the primary and secondary immunogenicity objectives (Figure 1).

Figure 1: Testing Sequence of the Primary and Secondary Objectives

At the first step in the testing sequence as demonstrated in [Figure 1](#), the noninferiority of mRNA-1010 compared with active comparator for A strains and for B strains will be tested at a type I error rate of 2.5% (2-sided) respectively.

If noninferiority is demonstrated for A strains only at the first step, the superiority testing for A strains will be tested following the order of testing sequence at a type I error rate of 2.5% (2-sided).

If non-inferiority is demonstrated for both A and B strains at the first step, the type I error rate for the following test will be 5% (2-sided).

The testing sequence can only continue to the next level if the tests at the higher level meet the success criteria (as specified in [Section 9.2](#)). If a test at the higher level fails to meet the success criteria for that level, the testing sequence will stop, and all testing thereafter will not be conducted.

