The study success can only be declared if the success criteria of the non-inferiority for both A strains and B strains are met.

Once the non-inferiority success criteria of the co-primary endpoints for A strains are met, hypothesis testing will continue (sequentially) based on α_1 as defined below to support secondary objectives, as follows.

Hypotheses in support of the secondary objectives will be tested at a two-sided $\alpha_1=5\%$ level if non-inferiority is demonstrated for both A and B strains (both H^1_0 and H^2_0 are rejected), and at an $\alpha_1=2.5\%$ level if non-inferiority is only demonstrated for A strains (only H^1_0 is rejected).

The null hypothesis H^3_0 : immunogenicity response to mRNA-1010 compared to that in participants who received the active comparator, as measured by GMR at Day 29 using HAI assay, is ≥ 1 for each individual A strain (H1N1 and H3N2). The superiority success criteria in immunogenicity response are met if H^3_0 is rejected at two-sided α_1 level. Based on GMT, superiority will be demonstrated by the lower bound of the $(100\% - \alpha_1)$ CI of the GMR ruling out 1 (lower bound > 1) for both A strains.

Once the success criteria of hypothesis H^3_0 are met, the next null hypothesis to be tested is H^4_0 .

The null hypothesis, H^4_0 : immunogenicity response to mRNA-1010 compared to that in participants who received the active comparator, as measured by GMR at Day 29 using HAI assay, is ≥ 1.5 for each individual A strain (H1N1 and H3N2). The super-superiority success criteria in immunogenicity response are met if H^4_0 is rejected at two-

sided α_1 level. Based on in GMT, super-superiority will be demonstrated by the lower bound of the $(100\% - \alpha_1)$ CI of the GMR ruling out 1.5 (lower bound > 1.5) for both A strains.

Once the success criteria of hypothesis H^4_0 are met, the last null hypothesis to be tested is H^5_0 .

The null hypothesis, H^5_0 : immunogenicity response to mRNA-1010 compared to that in participants who received the active comparator, as measured by SCR difference at Day 29 using HAI assay, is not super-superior for each individual A strain (H1N1 and H3N2). The super-superiority success criteria based on SCR are met if H^5_0 is rejected at two-sided α_1 level. Based on SCR, super-superiority will be demonstrated by the lower bound of the $(100\% - \alpha_1)$ CI of the SCR difference ruling out 10% (lower bound $> 10\%$) for both A strains.

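### Seroconversion is listed under the A-strain superiority objective, but the testing sequence has no step for a difference above zero; one can be added directly before H5 at no cost, with a gain confined to trials that pass H4 and fail H5

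*SAP*

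**What the plan says.** The secondary objective in Protocol section 3, Table 2 (also in the synopsis) is "To further evaluate the immunological response of mRNA-1010 (for superiority) relative to an active comparator against vaccine-matched influenza A virus strains at Day 29". Two endpoints stand under it: GMT, and "Proportion of participants reaching seroconversion at Day 29 as measured by HAI assay".

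Protocol 9.2 and 9.6.2, and SAP 4.2, 6.3.2 and 6.5, set the sequence that follows non-inferiority on the A strains. Each step must succeed on both A strains.

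- H3: lower bound of the GMR above 1.
- H4: lower bound of the GMR above 1.5.
- H5: "seroconversion rate difference ruling out 10% (lower bound $> 10\%$) for both individual A strains".

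SAP 4.2 describes the final step with "the last null hypothesis to be tested is H^5_0". SAP 6.3.2 heads it "Analysis of SCRs of anti-HA antibodies as measured by HAI against vaccine-matched influenza A strains on Day 29 (super-superiority testing") and makes it conditional on H4: "If super-superiority has been demonstrated based on GMT, the SCR of the vaccine-matched influenza A strains at Day 29" is compared between groups. If non-inferiority holds for both A and B strains, "the type I error rate for the following test will be 5% (2-sided"); if it holds for A strains only, α1 is 2.5%. SAP 6.5 treats every endpoint outside the sequence as descriptive and without multiplicity control.

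**The concern.** GMT and seroconversion are listed side by side under one superiority objective but are held to different standards. GMT can earn a superiority claim at zero margin and then a stronger one at 1.5. Seroconversion can earn only the stronger kind: SAP 4.2 words the criterion as "The super-superiority success criteria based on SCR are met if" H5 is rejected, and no step tests the difference against 0.

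At stake is a controlled claim on a listed secondary endpoint. If a trial passes H4 and both A strains show a precisely estimated seroconversion advantage that does not clear 10 points at the lower bound on both strains, the result can be described but not claimed within the controlled sequence. Non-inferiority on seroconversion and its reported 97.5% interval are unaffected.

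**Working it through.** **Inputs.** From SAP 4.3 and Protocol 9.3: 2550 per arm in the PP Immunogenicity Set (6000 × 0.85 = 5100, split 1:1), A-strain seroconversion 70% with true difference 0 (so a 70% comparator rate), SD 1.5 on the natural-log scale. From SAP 6.3.2: Miettinen-Nurminen interval, α1 of 5% or 2.5%. Assumed here: comparator rates other than 60% and 70%, independence of the two A strains, and the link from GMR to seroconversion in step 4.

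**1. The plan's own figure.** Non-inferiority on GMT: SE = 1.5 × √(2/2550) = 0.0420; ln(0.9/0.667) = 0.2996; power = Φ(0.2996/0.0420 − 2.241) > 0.9999 per strain. Non-inferiority on seroconversion: SE = √(2 × 0.7 × 0.3/2550) = 0.0128 at 70% and 0.0137 at 60%; power = Φ(0.10/SE − 2.241) > 0.9999 in each case. The stated 95% or more is reproduced.

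**2. Observed difference needed.** A search for the smallest observed difference whose Miettinen-Nurminen lower bound exceeds the margin gives:

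| Comparator rate | > 0, α1 5% | > 10, α1 5% | > 0, α1 2.5% | > 10, α1 2.5% |
|---|---|---|---|---|
| 50% | 2.75 | 12.75 | 3.18 | 13.10 |
| 60% | 2.71 | 12.59 | 3.06 | 12.98 |
| 70% | 2.51 | 12.35 | 2.86 | 12.67 |
| 80% | 2.16 | 11.88 | 2.47 | 12.16 |

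Hand check at 70% and α1 5%: near 82% in the other arm SE = 0.0118, and 10 + 1.96 × 1.18 = 12.3 points; near 72.5% SE = 0.0127, and 1.96 × 1.27 = 2.5 points.

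**3. Can a zero-margin step block H5?** A lower bound above 10 is also above 0, at the same α1 and with the same interval. In a grid check, all 19,221 outcomes that passed +10 also passed 0. H3 and H4 come earlier and are untouched.

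**4. How often would the step be reached and matter?** It is reached only after H4. H4 needs an observed GMR of 1.5 × exp(1.96 × 0.0420) = 1.63 (1.65 at α1 2.5%). Suppose seroconversion in the mRNA-1010 arm is Φ(Φ⁻¹(0.70) + ln(GMR)/s), where s is the assumed SD of the log fold-rise. At α1 5%:

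- True GMR 1.7: H4 power = [Φ(ln(1.7/1.5)/0.0420 − 1.96)]² = [Φ(1.02)]² ≈ 0.72.
- With s = 1.5 the seroconversion difference is 11.0 points (SE 0.0119); H5 power = [Φ((0.110 − 0.10)/0.0119 − 1.96)]² ≈ 0.02.
- With s = 1.2 the difference is 13.3 points (SE 0.0117); H5 power = [Φ((0.133 − 0.10)/0.0117 − 1.96)]² ≈ 0.65, taken alone.

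The gain is the chance that H4 passes and H5 fails, since power against 0 is essentially 100% at these differences. For s = 1.5, simulation of the sequence gave H4 in 0.73 of trials and H5 in 0.02, a gain of about 0.71. For s = 1.2, the gain is at least 0.716 − 0.653 ≈ 0.06 and at most 1 − 0.653 ≈ 0.35, depending on how the two tests correlate.

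Smaller true differences, same link and α1:

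| True difference | GMR (s = 1.2 / 1.5) | H4 power, both strains |
|---|---|---|
| 5 points | 1.20 / 1.25 | about 0 / about 0 |
| 8 points | 1.35 / 1.45 | about 0 / about 0 |
| 11 points | 1.53 / 1.70 | 0.4% / 71% |

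H4 power is a ceiling on the gain in each row.

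**The case against.** The strongest reply is that the step sits behind H4, so most modest seroconversion advantages would earn no claim even with it. That stands. A reader might take the stand-alone power against 0 at a true 5 points (0.98 per strain, 0.96 for both) as the benefit of the change. It is not, because under the SDs used here a difference of that size almost never comes with a GMR that clears 1.5. Without H4, even an observed advantage above 12 points earns no seroconversion claim, and the added step does not alter that.

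A reader might also infer that the seroconversion part of the objective has no hypothesis at all. The documents do not support this: H5 is a hypothesis on that endpoint, and passing it shows superiority by a margin. Nor do the protocol and SAP contradict each other; both use +10, and SAP 3.2 attaches the superiority label to GMT only. What is missing is a step at zero margin.

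The amendment summary says that the hypotheses and sequence were revised after regulatory agencies' comments on superiority. Those comments are not in the documents, so the margin-only test may have been deliberate. The proposal leaves H5 and its margin as they are.

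Finally, study success rests on non-inferiority alone, and the seroconversion difference is reported with its 97.5% interval in any case. This limits the importance of the point but does not supply a controlled superiority claim.

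**Conclusion.** The point holds as a gap between a stated objective and the tests that serve it. A trial that passes H4, with both A-strain seroconversion lower bounds above 0 but not both above 10 points, gets no controlled superiority claim on seroconversion. At a 70% comparator rate the threshold is about 12.4 observed points instead of 2.5 (12.7 instead of 2.9 at α1 2.5%).

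The practical gain from closing the gap depends on the true GMR and the fold-rise SD, which the documents do not give. At a true GMR of 1.7 and α1 5% it is about 71% of trials if the SD is 1.5, and somewhere between 6% and 35% if it is 1.2. At true differences of 5 or 8 points under either SD it is essentially nil. The plan itself is sized on a GMR of 0.9 and no seroconversion difference, so GMR 1.7 is an illustrative scenario. The primary conclusions are not affected.

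**What to change.** In Protocol 9.2 and 9.6.2 (with Figure 1) and SAP 4.2, 6.3.2 and 6.5, insert one step between H4 and H5. Its null is that the seroconversion difference is 0 or less for each A strain. Test it at α1 with the same Miettinen-Nurminen interval, and declare success if the lower bounds for both A strains exceed 0. Then test H5 against +10 points, unchanged.

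The cost is a few sentences, written before unblinding. Overall type I error is preserved because this is one more fixed-sequence step at the same α1, and no power is lost for H1 to H5. This depends on the placement. Ahead of H3 or H4 the step could block them: in simulation with a true GMR of 1.1 and a 70% comparator rate, H3 power fell from 0.38 to 0.14.

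If the sponsor prefers to keep a margin-only test, a sentence in Protocol section 3 and SAP 3.2 should say that superiority on seroconversion is assessed only against +10 points.

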6.3.3 Analysis of Exploratory Immunogenicity Endpoints

- Analyses of GMT and GMFR of nAbs by MN assays against vaccine-matched or vaccine-mismatched strains on Day 29, compared with Day 1 (baseline)
- Analyses of GMT and GMFR of anti-HA antibodies as measured by HAI against vaccine-mismatched strains on Day 29
- Analyses of GMT and GMFR of anti-HA antibodies as measured by HAI against vaccine-matched or vaccine-mismatched strains, on Day 181 and Day 361/EoS compared with Day 1 (baseline)

Descriptive statistics (n, median, min, max) will be provided for the following endpoints with corresponding 95% CI at each time point. The 95% CIs will be calculated based on the t-distribution of the log-transformed values then back transformed to the original scale for presentation. In addition, the GMT and GMFR with corresponding 95% CI will be plotted at each time point respectively.

The number and percentage of participants with an HAI titer $\geq 1:40$ post-injection due to vaccination at Day 181 and Day 361 will be provided with 2-sided 95% CI using the Clopper-Pearson method.

To further characterize the immune response to mRNA-1010 and active comparator, frequency, specificities, or other endpoints may be determined for further characterization of immune responses. A reverse cumulative distribution function plot of anti-HA antibody levels for HAI assay by visit will be provided.

6.4 Efficacy Analysis

The primary analysis population for efficacy is the mITT Set, unless otherwise specified. Participants will be included in the vaccination group to which they are randomized. The complete efficacy analysis will be performed once all participants complete the Day 181 visit or at the end of influenza season, whichever occurs later.

The evaluation of vaccine efficacy is a secondary objective in the study. The efficacy endpoint, RT-PCR-confirmed protocol-defined ILI and RT-PCR-confirmed CDC-defined ILI, are defined in [Section 3.2](#).

6.4.1 Analysis of Secondary Efficacy Endpoints

The vaccine efficacy of preventing the first episode of RT-PCR-confirmed protocol-defined ILI case and RT-PCR confirmed CDC-ILI case that begins at least 14 days post-vaccination through Day 181 or end of influenza season, whichever occurs later, caused by any strain of influenza virus will be evaluated.

6.4.1.1 Endpoint Definition/Derivation

If ILI symptoms have been reported from Day 1 to Day 361 (Month 12)/EoS, the investigator must contact the participant to assess symptoms using the ILI eCRF and ensure an NP swab is collected if the participant's symptoms meet the criteria for protocol-defined ILI or CDC-defined ILI. Detailed description of protocol-defined ILI and CDC-defined ILI are presented in [Section 3.2](#).

Both central laboratory RT-PCR results and local certified RT-PCR results will be used for case confirmation. More specifically, the following rules apply:

1. If at least one RT-PCR positive result is reported by either the central laboratory or a local certified laboratory, the RT-PCR result is considered as positive
2. The test collection date/time of positive result will be used in the analysis

CCI

CCI

Analysis of vaccine efficacy of RT-PCR-confirmed protocol-defined ILI are as follows:

The number and percentage of participants with RT-PCR-confirmed protocol-defined ILI will be summarized by vaccination group.

The incidence rate will be provided by vaccination group, calculated as the number of participants with a case (ie, first occurrence of ILI at least 14 days after the study injection through Day 181/end of influenza season) divided by the total person-time (years). The 95% CI of the incidence rate will be calculated using the exact method (Poisson distribution) and adjusted by person-time.

The relative vaccine efficacy (rVE) will be estimated by 1- the ratio of incidence rates (mRNA-1010 vs. active comparator) adjusting for person-time, multiplied by 100:

$$\text{rVE} = 100 \times \left(1 - \frac{\text{Incidence rate in mRNA-1010 group}}{\text{Incidence rate in active comparator group}}\right) \%$$

The estimated rVE of mRNA-1010 vs. active comparator will be provided with its 95% CI computed using the exact method conditional upon the total number of cases adjusted by the total person-time.

The person-time is calculated as the time from randomization to the date of the first episode for participants with a case, or the time from randomization to the date of discontinuation or death or Day 181/end of influenza season (whichever occurs later), whichever occurs first, for participants without a case.

The other secondary efficacy endpoints will be analyzed using similar methods:

- RT-PCR-confirmed CDC-defined ILI
- RT-PCR-confirmed protocol-defined ILI in participants aged 50 years and older
- RT-PCR-confirmed protocol-defined ILI in participants aged 65 years and older

Sensitivity analysis of these efficacy endpoints will be performed with the same methods described above based on the PP Set for Efficacy.

